6. OBJECTIVES AND OUTCOME MEASURES

Objectives	Outcome Measures	Timepoint(s) of evaluation of this outcome measure
Primary Objective To estimate prevalence of symptomatic and asymptomatic SARS-CoV-2 infection in the general population and how this varies over time	Presence or absence of SARS-CoV-2 virus assayed from a nose and throat swab	Every calendar day from the start of the study, with analysis based on continuous time and the latest test available in the prior 2 weeks
Secondary Objectives		
To estimate the incidence of new symptomatic and asymptomatic SARS-CoV-2 infection in the general population, and how this varies over time	Presence of SARS-CoV-2 virus in a nose and throat swab, separately in previously negative and previously positive individuals (to estimate re-infection after clearing the virus)	Every calendar day from the start of the study
To estimate immunity to SARS-CoV-2 in the general adult population and how this varies over time, as reflected by anti-S and anti- N immunoglobins (anti-N in all participants to protocol v15.0 only)	Optical density readings for anti-S(spike) and anti-N(nucleocapsid) IgG from a ELISA assay for SARS-CoV-2 antibodies assayed from blood, categorised according to predefined thresholds based on pre-pandemic plasma as positive or negative	Every calendar day from the start of the study, with analysis based on continuous time and the latest test available in the last month
To estimate the association between prevalence of symptomatic and asymptomatic infection in individual members of households	Presence or absence of SARS-CoV-2 virus assayed from nose and throat swabs taken from different members of the same household*	Each household visit
To estimate the association between immunity to SARS-CoV-2 across individual members of households	Concentrations and thresholds of IgG to SARS-CoV-2 assayed from blood of different members of the same households*	Each household visit

Objectives	Outcome Measures	Timepoint(s) of evaluation of this outcome measure
Exploratory Objectives To assess how prevalence and incidence of symptomatic and asymptomatic infection, and of immunity to SARS-CoV-2 (outcomes) varies by participant characteristics, particularly age, geographical location and time, but also other characteristics collected or linked including vaccination and cormorbidities or other characteristics from GP records and for prevalence and incidence of symptomatic and asymptomatic infection, how this varies by immunity to SARS-CoV-2, both natural and following vaccination	Presence or absence of SARS-CoV-2 virus assayed from a nose and throat swab Presence of SARS-CoV-2 virus in a nose and throat swab, separately in previously negative and previously positive individuals on nose and throat swabs (to estimate re-infection after clearing the virus), as assessed by immunity determined by IgG to SARS-CoV-2 assayed from blood, and by vaccination status and time from vaccination Concentrations and thresholds of IgG from an ELISA assay for SARS-CoV-2 antibodies assayed from blood	In individual cross- sectional surveys; repeated at each follow-up timepoint in those consenting to serial sampling
To assess how immunity to SARS-CoV-2, and having had SARS- CoV-2 infection, affects future use of NHS resources, development of specific conditions, and mortality	Inpatient admissions, outpatient attendances, A&E attendances, consultations with a General Practitioner, development of new conditions such as diabetes, heart failure, dementia and other conditions that could be related to SARS-CoV-2 infection as collected from available routine electronic NHS health records; overall mortality and cause of death as collected from ONS and relevant national mortality databases	Over time following each visit and after SARS- CoV-2 infection compared with not being infected, for up to fifteen years
To compare immunity to SARS-CoV-2 in the general adult population, as reflected by neutralising antibodies and IgG	Concentration of neutralising antibodies to SARS-CoV-2 assayed from blood, categorised according to predefined thresholds ¹⁴ as positive or negative Concentrations and thresholds of anti-S and anti-N IgG from an ELISA assay for SARS-CoV-2 antibodies assayed from blood	Specific study visits where neutralising antibody assays performed

Objectives	Outcome Measures	Timepoint(s) of evaluation of this outcome measure
To estimate the prevalence of "long	Repeated and continued reporting of	Over time
COVID" and whether this varies by	specific symptoms over time from a first	following each first
participant characteristics	positive swab test	positive swab; at
	Colf reported long COV/ID	cross-sectional
	Self-reported long COVID	visits
To estimate prevalence of other	Presence or absence of other respiratory	Every calendar day
respiratory infections in the general	viruses assayed from the same nose and	from the start of
population and how these vary over	throat swab as for SARS-CoV-2	sampling, with
time (depending on funding)		analysis based on
		continuous time
		and the latest test
		available in the
		prior 2 weeks

* estimated from statistical random effects models, see Section 11.

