((https://www.ukbiobank.ac.uk/media/zusjljce/ukb_serologystudy_report_month2_final-1.pdf)). From February 2021 to March 2022, all blood samples will also be tested for antibodies against the N (nucleocapsid) protein, rather than just the S protein, on the same sample as part of the single automated workflow. This should enable antibody responses to be categorised as against S only (compatible with vaccination) or against S and N (compatible with natural infection). Because anti-S is common to protection from both vaccination and natural infection, anti-S results will be returned to participants, but anti-N will not (this N-antibody test is currently for research uses only). From protocol v16.0, N-antibody will not be assayed on all samples due to capacity, but may be assayed in a subset determined either by random sampling, sampling according to date, or in specific groups of participants to test for missed infections. S-antibody results will be returned as positive or negative at the standard threshold used to identify those previously infected with SARS-CoV-2 vs not (based on plasma from prepandemic blood donors) as described above, in line with the MHRA CE marking for the test. However, this standard antibody threshold (42 ng/mL) was determined prior to vaccines being developed. This corresponds to 23.5 binding antibody units (BAU)/ml using the World Health Organization's (WHO) standardised units enabling comparison across different antibody assays. Currently, >97% of individuals are positive at this threshold²², meaning the vast majority get a positive result returned. A recent study

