© Copyright: The University of Oxford and Oxford University Hospitals NHS Foundation Trust 2019 Page 60 of 113 collaboration with Thermo Fisher Scientific as the OmniPATH Combi SARS-CoV-2 IgG Spike ELISA. In parallel the same sample will be tested for antibodies against the N (nucleocapsid) protein, as part of the same automated workflow. Up to protocol v15.0 all samples will be tested in parallel; from protocol v16.0, N-antibody will not be assayed on all samples due to capacity and funding, but may be assayed in a subset determined either by random sampling, sampling according to date, or in specific groups of participants to test for missed infections. The platform is capable of processing very small sample volumes often encountered with finger lance capillary sampling. Serum from a subset of samples will also be tested using neutralisation assays. These neutralisation assays use a lentiviral construct which expresses SARS-Cov2 S protein, and are tested in a cell-based system described as a pseudotype microneutalisation assay (pMN), as recently used in a study of Scottish blood donors.¹⁴ Any residual material (sera and spun cells) will be stored by the University of Oxford in secure facilities; it is not expected that there will be substantial residual material following capillary blood sampling, but any remaining sample will be stored and assay plates will be stored temporarily to enable assays to be re-run if necessary (e.g. if quality control issues are identified). Any residual material collected and stored in the study that, following analysis for the study, has been clearly identified as being of no further use, may be released to other researchers for use in COVID-19 related research projects, providing consent has been provided for samples to be stored and used in future research (explicitly requested, see Section 9.3).

In all laboratories, assay results will be returned to ONS identified only by the unique barcode and date of testing. Antibody results will be returned as the quantitative optical density readings for the ELISA assays and as positive/negative together with a half maximal inhibitory concentration in the positive group for the neutralisation assay through either a secure FTP site or an encrypted and password protected file. Nose and throat swab results will be returned as positive/negative and cycle threshold (CT) values, where available.

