11.7. The Level of Statistical Significance

A nominal significance level of 5% will be used; however, results will be interpreted based on their 95% confidence intervals rather than using a rigid threshold approach.

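### The neutralising-antibody outcome is cut to positive/negative although an inhibitory concentration is returned for positives; the information lost could be small or large

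*Protocol*

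**What the plan says.** Section 6 lists an exploratory objective: "To compare immunity to SARS-CoV-2 in the general adult population, as reflected by neutralising antibodies and IgG". Its outcome cell has two parts. The neutralising part is "Concentration of neutralising antibodies to SARS-CoV-2 assayed from blood, categorised according to predefined thresholds", ending in a positive or negative result, with a cited blood-donor study as the source of the thresholds. The IgG part is "Concentrations and thresholds of anti-S and anti-N IgG from an ELISA assay for SARS-CoV-2 antibodies assayed from blood", so the level is retained on that side.

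Section 9.9.1 says "Serum from a subset of samples will also be tested using neutralisation assays", without giving the size of the subset. It also says that antibody results reach ONS "as positive/negative together with a half maximal inhibitory concentration in the positive group for the neutralisation assay". A quantitative value therefore exists for positives, and negatives carry only the label.

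Section 11.1 states that there is no formal statistical analysis plan. Section 11.2 describes threshold-based models and also a regression on absolute optical density for IgG. It describes no analysis of neutralising antibodies.

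**The concern.** The two sides of one comparison are defined differently: IgG keeps its level, while the neutralising result is reduced to yes/no. A binary result can show whether the chance of neutralisation rises with IgG. It cannot show how the neutralising level changes with IgG among those who are positive.

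The protocol itself argues that level matters. Section 9.4.3 supports the quantitative IgG assay on the ground that higher levels may be needed against other variants. Section 9.6.1 adds a second, higher IgG threshold because the standard one predates vaccines. Neutralisation is run only in a subset, so each tested sample should yield as much as it can. At stake is the precision of this exploratory comparison; the primary and secondary objectives are not affected.

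**Working it through.** The protocol states no sample size, power or precision for this objective, so there is no figure to reproduce. The check asks how much information positive/negative carries relative to what the laboratory returns.

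**Inputs.** From the documents: positive/negative for every tested sample and an inhibitory concentration in positives only (Section 9.9.1); a binary outcome (Section 6). Assumed, because the documents do not give them: a normal distribution on the log scale; a fraction positive *p*; a correlation ρ with IgG; and a laboratory positive call that coincides with the predefined threshold.

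**Formulas.** Let *c* be the standard normal cut with fraction *p* above it, and φ the standard normal density at *c*. Per sample, relative to a value observed in everyone:

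- Binary outcome: φ² / [p(1 − p)]
- Data as returned (value above the cut, censored below): cφ + p + φ²/(1 − p)
- Loss = 1 − (binary / as returned)

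**Worked case, p = 0.5.** c = 0 and φ = 0.3989, so φ² = 0.159. Binary: 0.159/0.25 = 0.637. As returned: 0 + 0.5 + 0.159/0.5 = 0.818. Ratio 0.637/0.818 = 0.778; loss 22%.

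**Worked case, p = 0.9.** c = −1.2816 and φ = 0.1755, so φ² = 0.0308. Binary: 0.0308/0.09 = 0.342. As returned: −0.225 + 0.9 + 0.308 = 0.983. Ratio 0.348; loss 65%.

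| Fraction positive | Binary | As returned | Loss |
|---|---|---|---|
| 10% | 0.342 | 0.359 | 4.7% |
| 30% | 0.576 | 0.655 | 12.1% |
| 50% | 0.637 | 0.818 | 22.2% |
| 70% | 0.576 | 0.921 | 37.5% |
| 90% | 0.342 | 0.983 | 65.2% |
| 97% | 0.159 | 0.996 | 84.0% |

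The loss passes one third at about 65% positive.

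**Stronger association.** The table holds for a weak association with IgG. For larger ρ, the slope variance was compared between probit (binary) and Tobit (as returned) models:

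| ρ | 10% | 30% | 50% | 70% | 90% |
|---|---|---|---|---|---|
| 0.5 | 8% | 18% | 30% | 47% | 73% |
| 0.7 | 14% | 28% | 41% | 58% | 80% |
| 0.9 | 36% | 52% | 64% | 76% | 90% |

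In terms of samples, with a weak association and 50% positive, 100 samples analysed as yes/no carry what about 78 would carry as returned. At 90% positive they carry what about 35 would.

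**The case against.** The strongest defence is that the wording does not prove the values are discarded. The cell begins with the concentration. The secondary IgG outcome in Section 6 is likewise described as optical density categorised against thresholds, yet Section 11.2 models that density on its absolute scale. Part of this stands: categorising in Section 6 does not forbid a quantitative analysis. But the IgG value is restored by explicit text in Section 11.2, and nothing does the same for neutralisation.

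It is also fair that a predefined cut-off is a legitimate summary, that the objective is exploratory, and that no test or sample size is attached to it. Section 11.7 says "A nominal significance level of 5% will be used" but puts interpretation on confidence intervals. The loss is therefore better read as precision than as power.

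Three stronger readings are tempting, and the documents do not support them:

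- **The cut loses at least a third of the information.** The textbook figure 1 − 2/π = 36% compares a median cut with a value measured in everyone. Here negatives have no value, so that comparator does not exist. Against the data returned, the loss can be as low as about 5%.
- **Nearly everyone is positive on neutralisation.** Section 9.6.1 says "Currently, >97% of individuals are positive at this threshold", but that is anti-S IgG at its own threshold. No neutralising positivity is given.
- **Only agreement between two yes/no results is possible.** IgG is kept as a concentration, so neutralising status can still be related to IgG level.

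Whether the cited threshold suits vaccinated people cannot be judged from the protocol.

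**Conclusion.** The point holds as a minor one. The stated outcome drops a quantitative value that the laboratory already returns for positives, while the IgG side of the same comparison keeps its level. With a weak association, the loss against the data returned runs from about 5% at 10% positive to 84% at 97%; over 10–90% positive and ρ up to 0.9 it runs from about 5% to 90%. These figures rest on a normal log scale and on assumed positivity and correlation, so the protocol supports a range and no single figure. If few samples are positive, little is lost; if most are, well over half may be. No contradiction in the protocol is shown, and its main objectives are untouched.

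**What to change.** In Section 6, state the neutralising outcome for this comparison as log half-maximal inhibitory concentration, with negatives left-censored at the assay limit below which no value is returned. Add one sentence to Section 11.2 naming the model: Tobit or interval regression of that outcome on log anti-S level. Keep positive/negative at the predefined threshold as a secondary summary.

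The cost is a change of wording and one extra model. The downside is a distributional assumption on the log scale, which matters more when many samples are negative; the binary summary, reported alongside, does not depend on it.

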- Email if participant would like to receive communication about the study (eg assessment window notifications) or test results (results will be returned by the study identified by month and year of birth only (not person-identifiable), or vouchers for participation directly by this route, and also to receive updates on results and news about the study (see Section 16.8). Participants may opt out of emails with updates on results from and news about the study, but may not opt out (unsubscribe) from emails about the study procedures or test results, or any communication about the study that has been approved by the Research Ethics Committee.

The following questions will be asked at each assessment (including the enrolment home visit up to protocol v15.0 and the first time the questionnaire is completed online or by telephone for new participants from protocol v16.0), with only changes (where relevant) being elicited at any follow-up assessments:

- Is the participant currently symptomatic or self-isolating? If self-isolating is this because of symptoms in self or others in the household
- Do they have any of the following symptoms today (yes/no for each of fever (including high temperature), muscle ache (myalgia), fatigue, sore throat, cough, shortness of breath (dyspnea), chest pain, headache, nausea/vomiting, abdominal pain, diarrhoea, loss of taste, loss of smell,

Clinical Research Protocol Template version 15.0

© Copyright: The University of Oxford and Oxford University Hospitals NHS Foundation Trust 2019 Page 56 of 113 trouble sleeping, loss of appetite/eating less than usual, runny nose/sneezing, noisy breathing (wheezing), chest pain, palpitations, vertigo/dizziness, memory loss/confusion, difficulty concentrating, worry/anxiety, low mood/not enjoying anything, other symptoms) or since the last visit, or otherwise consider that they currently have COVID-19

- Have they recently been in contact with someone that they definitely know (based on a positive test) or suspect (no positive test) was infected with COVID-19 at the time of contact? Yes/No for each type of contact and for each
 - If yes, date of last contact
 - o If yes, was this someone in their own household or someone outside their household
- Occupation (available from ONS or NISRA for the adult targeted in the original letter where identified from previous surveys, but not for the rest of the household or those identified through address lists)

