- Working status (employed, not working, retired, student etc) and work location (at home, outside of home etc), including number of days per week usually spent working outside the home or at school/nursery, and mode of transport to get to work/school/nursery
- Healthcare and social care contacts including currently working in health/social care in roles which primarily directly interact with patients/residents/clients or not, recently visited hospital or residential/nursing care home
- Contacts with other individuals inside the household (eg social distancing within the household) and outside the household, including through work, school/nursery, shopping, exercise etc including duration and number of individuals, how easy they find it to maintain social distancing and use of face coverings or masks
- Do they have long-term health problems, and do these limit their activities?
- Current smoking status
- Have they recently travelled abroad? If yes, to which countries?
- Have they received or been offered a vaccine against COVID-19? If yes, type, number of doses, dates.
- Have they received a vaccine against influenza? If yes, date.
- Do they think/know they have been infected by COVID-19? Yes/No
 - If yes, date first symptoms and what symptoms (yes/no for each of fever (including high temperature), muscle ache (myalgia), fatigue, sore throat, cough, shortness of breath (dyspnea), chest pain, headache, nausea/vomiting, abdominal pain, diarrhoea, loss of taste, loss of smell, trouble sleeping, loss of appetite/eating less than usual, runny nose/sneezing, noisy breathing (wheezing), chest pain, palpitations, vertigo/dizziness, memory loss/confusion, difficulty concentrating, worry/anxiety, low mood/not enjoying anything, other symptoms)
 - \circ If yes, did they contact the NHS about this (suspected) COVID-19 infection? Yes/No
 - If yes, were they tested? Yes/No
 - If tested, were they positive/negative/test failed/results not yet received?
 - If yes, were they hospitalised Yes/No?
 - If yes, do they think that they are suffering from "long COVID" and with what symptoms?
 How is this limiting their activities?

Household postcode (required at the level of outward portion and first number of the inward portion for geospatial analyses) will be available from the original ONS or NISRA survey or the address list from which the household was sampled. However, full address will also be confirmed against the household

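### The symptom-based long COVID measure has no uninfected comparator and no pre-infection baseline, so persistent background symptoms after a positive swab count as long COVID

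*Protocol*

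**What the plan says.** The outcome table in protocol Section 6 includes an exploratory objective: the prevalence of long COVID and whether it varies by participant characteristics. It gives two measures.

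- Symptom-based: "Repeated and continued reporting of" "specific symptoms over time from a first" positive swab test, evaluated over time after each first positive swab.
- Self-report: "Self-reported long COVID", at cross-sectional visits.

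For the first measure the table gives no comparison group, symptom baseline before infection, minimum duration, number of reports or named subset of symptoms.

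Section 9.6.1 describes how the data arise. The symptom items fall under the statement "The following questions will be asked at each assessment", so they go to all participants whatever their swab result. The list has 23 distinct named symptoms (chest pain appears twice) plus an open category. It runs from fever and loss of smell to fatigue, headache, trouble sleeping and "difficulty concentrating, worry/anxiety, low mood/not enjoying anything, other symptoms". The self-report item is asked only of those who think or know they have been infected: "do they think that they are suffering from 'long COVID' and with what symptoms".

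Section 11.2 describes no long COVID analysis, and Section 11.1 says there is no formal statistical analysis plan.

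**The concern.** Many of the listed symptoms are common and long-lasting in people who have never had COVID-19. A measure that starts the clock at a positive swab and counts continuing symptoms cannot separate symptoms caused by the infection from symptoms the participant already had or would have had anyway.

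Two results are exposed. The first is the level: the share of swab-positive participants with infection-attributable persistent symptoms is overstated whenever the background share is above zero. The second is the comparison by participant characteristics, which is half of the objective. A group with more background symptoms will show more long COVID even if infection adds the same risk in every group.

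The protocol applies the right logic elsewhere in the same table. The objective on NHS use, new conditions and mortality is evaluated after "CoV-2 infection compared with not being infected, for up to fifteen years". Section 7 also provides for linkage back to January 2016, so that conditions present before joining can be adjusted for. The long COVID objective has neither safeguard.

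**Working it through.** **No figure to reproduce.** The protocol gives no prevalence, precision or sample-size figure for long COVID. The check is textual, followed by an illustration on assumed values.

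**1. Is a comparator stated anywhere?**
- Section 6, long COVID rows: none.
- Section 6, NHS use, new conditions and mortality: yes, against not being infected.
- Section 11.2: the only comparison of ever-positive with never-positive participants concerns predictors of testing positive, not symptom persistence.
- Section 11.2 also refers to an external methods page, which is not available here.

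**2. Are the data for a comparator collected?** Yes. Section 9.6.1 asks the symptom items of everyone at each assessment, and Section 11.2 provides for linked test results from national databases.

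**3. Direction and illustrative size.** Let b be the share with a qualifying persistent symptom from other causes, and e the share with one because of infection. Both are assumptions, taken as independent. The crude measure is

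A = 1 − (1 − b)(1 − e).

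The excess over uninfected controls is A − b = e(1 − b). Dividing by (1 − b) returns e. With e = 5%:

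| b | Crude A | A / e | Share of cases not attributable, (A − e)/A | Excess A − b | (A − b)/(1 − b) |
|---|---|---|---|---|---|
| 1% | 5.95% | 1.19 | 16% | 4.95% | 5.0% |
| 3% | 7.85% | 1.57 | 36% | 4.85% | 5.0% |
| 5% | 9.75% | 1.95 | 49% | 4.75% | 5.0% |
| 10% | 14.5% | 2.90 | 66% | 4.50% | 5.0% |

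Over b = 1–10% and e = 2–10%, the ratio A/e runs from 1.09 (b = 1%, e = 10%; A = 10.9%) to 5.90 (b = 10%, e = 2%; A = 11.8%). The share not attributable runs from 8% to 83%. A range this wide shows that the size is not known; it is not an estimate of it.

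**4. Effect on subgroup comparisons.** Take two groups with the same e = 5% but b = 1% and b = 10%. The crude measure gives 5.95% and 14.5%, an apparent ratio of 14.5/5.95 = 2.4 with no difference in the effect of infection. The excesses are 4.95% and 4.50%, and the rescaled values are both 5.0%.

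**5. Effect of undetected infection in controls.** If a share c of controls were infected without detection, with the same e, their rate is b + c·e(1 − b). The excess becomes e(1 − b)(1 − c), so it is too small by the factor (1 − c). The loss is slight only if c is small.

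**The case against.** The case on the other side has several parts.

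- **An outcome table says what is measured and when, and silence on a comparator is not a decision against one.** This stands in part, since the external methods page might contain a comparison. But the same table names the uninfected comparison where it is intended, and the protocol says there is no formal analysis plan to supply it. Followed as written, the measure is uncontrolled.
- **Repeated and continued reporting of specific symptoms is narrower than any report of any listed item.** This stands as a limit on size. Those words would remove some transient symptoms, but none of them is defined, and they do not remove chronic background symptoms.
- **There is a second measure.** True, so the point concerns one measure of two. Self-report does not repair the first: it has no comparator either, and it rests on what participants believe caused their symptoms.
- **The objective is exploratory.** True. The primary and secondary objectives are untouched.
- **Reporting an excess changes the quantity estimated.** This is fair, and is why the crude proportion should be kept alongside it.

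Stronger readings are tempting but unsupported. A reader might infer a large inflation from the length of the list. If each of 24 items had an independent background rate of 0.5–2%, then 1 − (1 − p)^24 gives 11–38% with at least one symptom. That is a single-visit figure, and the outcome requires repeated reporting. The same independence assumption for one symptom at two visits, 1 − (1 − p²)^24, gives only about 0.06–1.0%. Neither figure describes this outcome, because chronic symptoms are not independent between visits.

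A reader might also infer that the population prevalence of long COVID is overstated on balance. The documents do not show that either. Anchoring on a positive study swab misses infections before enrolment and between visits, which pulls population prevalence down.

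**Conclusion.** The concern holds for the symptom-based measure of one exploratory objective. As written, persistent background symptoms after a first positive swab count as long COVID. The measure therefore overstates the share of swab-positive participants with infection-attributable symptoms, and differences by participant characteristics may partly reflect background symptoms.

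The direction follows from the definition whenever the background share is above zero. The size cannot be found from the documents. The factors of 1.09 to 5.90 rest wholly on assumed background and attributable shares and on independence between them. The conclusion also assumes that no comparison is specified on the external methods page.

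**What to change.** Keep the crude proportion, and add to Section 6 and Section 11.2 a controlled estimate as the symptom-based result:

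1. Fix the definition: which symptoms, how many reports and over what period.
2. Apply the same definition to participants with no prior positive study swab, no positive linked test and, where measured, no positive anti-N result. Give each an index date, matched on age, sex, region, calendar month and visit schedule. Schedule matters because weekly and monthly assessments offer different chances to report a symptom repeatedly.
3. Account for symptoms reported before the index date in both groups. Participants positive at their first assessment have no earlier study report and should be shown separately.
4. Report the excess over controls, overall and by participant characteristics.
5. Report by calendar period.

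The cost is analysis work only, with no new data collection. The downside is undetected infection among controls, which makes the excess conservative. This may be more than slight from April 2022, when Section 5 restricts anti-N to a subset. Anti-S cannot fill the gap: Section 9.6.1 reports more than 97% positive at the standard threshold, and vaccination also produces these antibodies. Reporting by period lets the reader see where the controls are least reliable.
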